Exclusion criteria include: presence of a cardiac pacemaker or presence of any other implanted electrical stimulation device, uncontrolled hypertension (SBP>170 mmHg), unstable angina, heart attack within the last month, expected survival <6 months, unsuitable for participation based on physician assessment, unwilling or unable to give informed consent.

4. Outcome measures.

4.1 Primary Outcome.

The primary outcome measure will be the change in insulin resistance as determined by either HOMA-IR or LAR after 8 and 16 weeks of EMS training. The analysis will also be stratified by whether patients achieved optimum dialysis care goals at randomization to see if optimization of care influenced the response to EMS. The correlation between change in HOMA-IR or LAR with change in aerobic capacity (peak VO₂) and quadriceps strength after 16 weeks training and with maximal EMS training intensity (in mV) achieved will be assessed to determine if change in insulin resistance depends on intensity of training.

4.2. Secondary outcomes measures.

4.2.1. Aerobic capacity and quadriceps strength. The effect of EMS on quadriceps muscle strength will be assessed 5 times (Visits 1, 2, 9, 12 and 14 in Figure 1) : at baseline, pre-EMS training, at 8 and 16 weeks of EMS training and again 4 weeks after stopping EMS training. Quadriceps muscle strength will be determined using a belt-stabilized portable dynamometer.⁴³ Change in peak VO₂ will be measured 3 times (Visits 2, 9 & 12): pre-EMS training and after 8 and 16 weeks of EMS training. Peak VO₂ will be determined using graded exercise treadmill test using a Balke protocol. Cycle ergometry will be used to determine peak VO₂ in patients who can't walk on a treadmill but can do cycling. This will determine if EMS produced an increase in quadriceps strength or improvement in aerobic capacity after 8 and 16 weeks of training. It will also determine how rapidly the effect on muscle strength is lost after stopping EMS training.

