4.2.2. Body and leg composition changes. The effect of EMS on total body fat and lean mass, visceral fat mass and regional thigh fat and lean mass will be determined by DXA scanning. DXA scanning will be done 3 times: pre-EMS training and after 8 and 16 weeks of EMS training. The DXA results will be supplemented by measuring the effect of EMS on anthropometric measures including: body mass index (BMI), waist (minimal circumference) to hip (maximal gluteal protuberance) ratio, anterior-posterior diameter at the umbilicus and thigh circumference (1/2 way between the anterior iliac crest and upper border of the patella, bilaterally). The anthropomorphic studies will be performed 5 times: at baseline, pre-EMS, after 8 and 16 weeks of EMS training and 4-weeks after stopping training. Collectively these studies will determine whether EMS had an effect on body fat or muscle composition. Of particular interest is change in visceral/abdominal fat and change in quadriceps muscle mass after 8 and 16 weeks of EMS training.

4.2.3. Measures of physical activity. Changes in physical activity will be assessed at 5 time points: baseline, pre-EMS, after 8 and 16 weeks of EMS training and 4 weeks after stopping EMS training using a standardized 6-minute walk test and by monitoring 48 hour activity level between dialysis sessions using a wristwatch activity monitor. The 6-minute walk test is determine by measuring the distance a patient can walk on a standardized track within 6 minutes at whatever pace they choose to walk.

4.2.4. Malnutrition-inflammation (MIS) assessment. The MIS is a 10 item test which includes assessment of change in patient dry weight over 3-6 months, dietary intake, gastrointestinal symptoms, functional capacity, major co-morbidities, decreased fat mass, signs of muscle wasting, BMI, serum albumin and serum TIBC.⁴⁴ It has been validated as a predictor of mortality in hemodialysis patients.^{44,45} MIS will be assessed at 5 time points: baseline, pre-EMS, after 8 and 16 weeks of EMS training and 4-weeks after completion of EMS training.

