8. Statistical analysis/Power calculations.

This is a pilot feasibility and preliminary efficacy study to determine whether EMS can be delivered to this population and to assess the magnitude of the change and variability in the primary and secondary outcome measures. Data derived from this study will allow planning of a larger randomized controlled study. We plan to recruit up to 15 patients into the trial and complete the trial within 1 year. There will be 5 measurements of the primary and most of the secondary outcome variables in each patient. These will be performed at enrollment, after 4 weeks of "dialysis care

optimization" before starting the EMS intervention, then at 8 and 16 weeks after initiation of the EMS intervention and finally 4 weeks after stopping EMS. The DXA scan, measurement of peak VO₂ will only be performed three times (before starting EMS and then again at 8 and 16 weeks of EMS training). The optional muscle biopsy for gene expression analysis will be performed up to 4 times in patients who agree to this analysis (before and after the first EMS treatment, at 8 and 16 weeks of EMS training). Summary statistics will be used to describe and analyze the data. Changes over time in the outcome variables will be analyzed using the Friedman analysis of variance by ranks to determine if there was a statistically significant effect of EMS. A P<0.05 will be considered statistically significant. Regression analysis will be used to determine if the change in HOMA-IR or LAR is correlated with the magnitude of the observed exercise training effect (i.e. the increase in peak VO₂ or quadriceps muscle strength at 4 months) or maximum intensity of EMS stimulation used during training.

Based on an estimated baseline mean (\pm SD) HOMA-IR score of 4.8 (\pm 1.7) mg/dl· μ U/ml, a sample size of 15 patients will provide 80% power to detect a 28% decrease in the HOMA-IR score (by a paired t-test analysis) at the P=0.05 level. This decrease in HOMA-IR score would be predicted to be associated with a clinically significant reduction in mortality.³³

9. Selected methods

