In Affymetrix Human Exon 1.0 ST arrays, the log2 hybridization signal reflects the mean signal intensity of all exon probes specific for an individual mRNA, and is proportional to the level of that mRNA. We will perform two main comparisons: 1) the effect of acute exercise comparing the gene expression levels 4 hours after the first EMS training to baseline before training and 2) the effect of chronic EMS training (8 and 16 weeks) compared to the Pre-EMS training sample. We will restrict the analysis to mRNA's that have a mean log2 hybridization signal of >5 in either the pre-EMS sample or the 8 or 16 week EMS treatment conditions. We will use paired t-tests to determine which of the remaining mRNA's are present at a significantly different level (adjusting for the false discovery rate inherent in multiple testing) in the EMS treatment compared to the baseline sample. The list of differentially expressed genes will be examined for important biological pathways relating to muscle glucose metabolism and insulin response, mitochondrial biogenesis and function, muscle phenotype, growth and energy metabolism, oxidant stress and inflammation. We will also use bioinformatics tools such as Onto-Express to help translate the list of differentially expressed genes into functional categories such as biological process or cellular role based on the annotation using Gene Ontology terms. All microarray data will be deposited in the GEO database.

10. References

1. U.S. Renal Data System, *USRDS 2012 Annual Data report: Atlas of End-Stage Renal Disease in the United States*, National Institutes of Health, National Institute of Diabetes and Digestive and Kidney Diseases, Bethesda, MD, . 2012.
2. Carrero JJ, de Jager DJ, Verduijn M, et al. Cardiovascular and noncardiovascular mortality among men and women starting dialysis. *Clin J Am Soc Nephrol*. Jul 2011;6(7):1722-1730.
5. Johansen KL. Exercise in the end-stage renal disease population. *J Am Soc Nephrol*. Jun 2007;18(6):1845-1854.

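### About 25 secondary outcomes are each tested at P<0.05 for an EMS effect with no testing order or adjustment; if nothing changes over time, the chance of at least one significant result is about 36% to 70%, depending on correlation

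*Combined protocol and SAP*

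**What the plan says.** Section 8 (Statistical analysis/Power calculations) gives a single inferential rule: "Changes over time in the outcome variables will be analyzed using the Friedman analysis of variance by ranks", and the stated purpose is "to determine if there was a statistically significant effect of EMS". The threshold follows at once: "A P<0.05 will be considered statistically significant". The rule is not confined to the primary outcome. The same section says "There will be 5 measurements of the primary and most of the secondary outcome variables in each patient", while DXA and peak VO₂ "will only be performed three times".

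The secondary outcome sections describe what these data will settle in firm terms. Section 4.2.1, on strength and aerobic capacity: "This will determine if EMS produced an increase in quadriceps strength or improvement in aerobic capacity after 8 and 16 weeks of training". Section 4.2.2, on DXA and anthropometry: "Collectively these studies will determine whether EMS had an effect on body fat or muscle composition".

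Multiple testing is addressed in one place only, Section 9.8 on gene expression: "adjusting for the false discovery rate inherent in multiple testing".

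Section 8 also opens by describing the trial as a pilot of feasibility and early efficacy. Its data on size and variability of change, in primary and secondary measures alike, are to support planning of a larger randomized trial.

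**The concern.** A P<0.05 rule applied once per variable to a long list will produce some significant results by chance, and Section 8 says how such a result is to be read: as an effect of EMS. Nothing in the plan says how many such results to expect, which variables come first, or that the secondary tests carry less weight than the primary one. A report that follows the plan literally could present a chance finding in, say, one oxidative stress marker as a demonstrated effect. Because the next step is a randomized trial, such a finding might also colour the choice of endpoints there.

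This point is about the secondary family. How HOMA-IR and the leptin-adiponectin ratio share the primary role is a separate matter.

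**Working it through.** **Is there a figure in the plan to reproduce?** Not for this point. Section 8's only calculation is the power for HOMA-IR: 15 patients, 80% power, a 28% fall from 4.8 (SD 1.7) by paired t-test. That reproduces: the difference is 0.28 × 4.8 = 1.344, and with the SD of change taken as 1.7 the two-sided power is 81.2%. It says nothing about the secondary outcomes, and the plan states no family-wise error rate.

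**Step 1: count the variables.**

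| Section | Variables | Number | Visits |
|---|---|---|---|
| 4.2.1 | Peak VO₂ | 1 | 3 |
| 4.2.1 | Quadriceps strength (legs combined) | 1 | 5 |
| 4.2.2 | DXA: total fat, total lean, visceral fat, thigh fat, thigh lean | 5 | 3 |
| 4.2.2 | BMI, waist-hip ratio, anterior-posterior diameter, thigh circumference | 4 | 5 |
| 4.2.3 | 6-minute walk, activity monitor | 2 | 5 |
| 4.2.4 to 4.2.6 | MIS, PHQ-9, KDQOL-36 (one score each) | 3 | 5 |
| 4.2.7 | IL-6, TNFα, CRP | 3 | 5 |
| 4.2.8 | F2-isoprostane, protein thiols, GSH/GSSG, GPx, SOD, CAT | 6 | 5 |

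Total: 1 + 1 + 5 + 4 + 2 + 3 + 3 + 6 = 25, of which 6 have three visits and 19 have five. Left out are the anemia and mineral data (4.2.9 and 4.2.10, described as plotted) and the blood pressure, pulse and hypotension comparisons (4.2.11). Testing legs or questionnaire subscales separately would add to the count. The anterior-posterior diameter is named in 4.2.2 but is not in the visit checklists of Section 5; dropping it leaves 24.

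**Step 2: independent tests.** With exact 5% tests, the chance of at least one P<0.05 is 1 − 0.95^25 = 72.3% (1 − 0.95^24 = 70.8% for 24), and 25 × 0.05 = 1.25 false positives are expected. At n=15 the chi-square Friedman test is slightly conservative, with a simulated size of about 4.7%. This gives 1 − 0.953^25 ≈ 70% and 25 × 0.047 ≈ 1.2 expected.

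**Step 3: correlated outcomes.** Many of these variables will move together (fat measures, cytokines, antioxidant enzymes), so independence is an extreme. I simulated 20,000 trials per setting with 15 complete patients. At each visit, each outcome was √ρ × a shared normal term + √(1−ρ) × its own normal term, with no change over time. The chi-square Friedman test was applied at 0.05 to 19 outcomes with five visits and 6 with three.

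| Assumed correlation ρ | At least one P<0.05 | Two or more |
|---|---|---|
| 0 | 70% | 33% |
| 0.3 | 63% | 30% |
| 0.5 | 54% | 27% |
| 0.7 | 43% | 24% |
| 0.8 | 36% | 20% |

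The expected number of false positives is about 1.2 in every row, because correlation changes how they cluster and not how many there are on average. The documents give no correlation, so the range is the result and no single row is.

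**The case against.** The best defence is the pilot framing. Section 8 itself says the aim is to learn the size and variability of change, and it names the secondary measures when it says so. A reader would know that these are early results, and a randomized trial is meant to follow. The plan also signals priorities. Section C.1 uses peak VO₂ and quadriceps strength to judge the training and lists the rest as additional measures. Section A stresses visceral fat, and Section 4.2.2 singles out abdominal fat and quadriceps mass. This stands, and it lowers the severity. It would be wrong to say that the plan has no exploratory framing or no sense of rank. But neither the framing nor the priorities reach the testing rule, which stays the same for every variable and ends in a declared effect.

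Some stronger readings are tempting and are not supported:

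- A reader might infer that a false positive is more likely than not. That holds only up to a correlation of roughly 0.5, and the documents supply no correlation.
- A reader might infer that these are the error rates for an inert device. The simulation assumes no change over time for any reason. The five measurements span a 4-week care optimization phase, and patients are encouraged to exercise outside dialysis. With no control group, a Friedman test could be significant through such changes even if EMS did nothing, and no multiplicity adjustment would remove that.
- A reader might speak of false benefits or harms. The Friedman test is an omnibus test without direction.
- A reader might infer that the plan breaches a 5% family-wise limit or will pick the next trial's endpoints by P-value. It states no such limit, and it speaks of planning from size and variability.

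**Conclusion.** The concern holds in a limited form. About 25 secondary variables fall under a single P<0.05 rule that is read as an EMS effect, with no formal order and no adjustment, although the plan accepts the need for adjustment in its gene expression work. If no outcome changes over time, the chance of at least one significant result is about 36% to 70%, with about 1.2 expected. This rests on 15 patients with complete data, the count above, and an assumed common correlation between 0.8 and 0. The consequence is modest: this is a pilot, and the damage is confined to how secondary results are described. Attribution of change to EMS in a single-arm design is a further weakness that this point does not address.

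**What to change.** Three wording changes:

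1. In Section 8, limit the sentence "A P<0.05 will be considered statistically significant" to the primary outcome.
2. In Section 8, add that all Section 4.2 outcomes are exploratory. They will be reported as estimated change from the pre-EMS visit with unadjusted 95% confidence intervals, and no claim of a statistically significant EMS effect will be made for them.
3. In Sections 4.2.1 and 4.2.2, replace 'determine' with 'explore' in the two sentences quoted above.

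Estimates with intervals also serve the pilot's stated aim better than a list of significance verdicts. Taking the pre-EMS visit as reference leaves the care optimization interval out of the estimated change, but it does not turn that change into a controlled comparison.

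If the sponsor wants P-value claims for secondary outcomes, the false-discovery-rate approach already used in Section 9.8 could be applied to the listed outcomes instead. This is optional.

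The cost is small: no new patients, visits or data. The downside is that fewer secondary results can be called statistically significant.

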Following enrollment, baseline data and selected outcome markers will be assessed. Then all patients will undergo a 4-week care optimization phase during which time we will review the patient's dialysis care and make adjustments (if necessary) to meet standard of care guidelines as defined by CMS, KDOQI and KDIGO (Table 1). Outcome markers will be reassessed again after completion of the 4-week care optimization phase. At this time all patients will also undergo a baseline exercise test to measure peak VO₂ and a DXA scan for body composition analysis before starting EMS training.

| Table 1 | |
|---------------------------|--|
| Parameter | Optimized care goals |
| Vascular access | Discontinuation of central venous catheter and use of arteriovenous access |
| Fluid removal | Optimize dry weight. Limit UF rate to ≤ 13 ml/kg/hr |
| Solute removal | Minimum dialysis time ≥ 3.5 hours. Goal 4 hours. kT/V ≥ 1.4 |
| Acid-base | Pre-dialysis HCO ₃ between 22-27 mEq/L |
| Anemia | Hemoglobin 9.5-11 g/L, if on erythropoietin; Iron saturation $\geq 20\%$ |
| Ca, PO ₄ , PTH | Calcium, PO ₄ within normal levels; PTH ≤ 600 pg/ml |

EMS training will be done while the patient is on hemodialysis. At the first EMS training session, optimal EMS settings will be established and patients will be taught how to apply the electrodes and use the muscle stimulator. For patients who agree we will also do a muscle biopsy of the quadriceps (vastus lateralis) muscle at this first training visit before starting EMS training. Patients will be seen at the next dialysis session and again after 7 days to confirm that they are doing the EMS training properly. Patients are then seen at Day 14, 28, 42, 56, 84 and 112 after starting EMS training to assess for any adverse events, monitor progress with EMS training and adjust the EMS settings to make sure they are at the optimal tolerated intensity of muscle stimulation. The EMS training will continue for 16 weeks. At Day 56 and Day 112 (8 and 16 weeks) of EMS-training all the primary and secondary outcome variables including exercise stress test for peak VO₂ and DXA scan will be performed. For patients who agree we will also perform a muscle biopsy at a dialysis visit around Day 56 and Day 112 (not the same day as the exercise stress test). One month after stopping EMS training the patient will be seen and the outcome variables will be repeated except for the DXA scan and the exercise stress test.

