4.2.11. Blood pressure and dialysis hypotension. Maintenance of blood pressure on dialysis can be a challenge for some patients, particularly those with large intra-dialytic fluid gains, and is associated with poor outcomes.⁶⁹ A prior study of EMS during hemodialysis found that EMS produced a statistically significant increase in BP and fewer hypotensive episodes compared to no EMS.²⁹ For the first EMS treatment in each patient we will directly record BP and pulse at 15-minute intervals before, during and after treatment with EMS. Thereafter, we will collect the BP and pulse data that is recorded (approximately every 15-30 minutes) as standard of care for every hemodialysis session. We will compare the average hemodialysis BP and pulse during the 4-week “care optimization” phase to that obtained during the EMS treatment and the 4-week post-EMS treatment phases to determine if EMS was associated with any change in BP or pulse. We will also analyze the frequency of dialysis sessions with a hypotensive episode (defined as SBP<90 mmHg or need for IV saline for hypotensive symptoms) during EMS compared to non-EMS treatment.

4.2.12. Muscle gene expression. Gene expression profiling of mRNA extracted from a skeletal muscle biopsy will be performed to give insight into the biological pathways activated by EMS both acutely and with chronic training in hemodialysis patients. Patients will be allowed to opt out of any of the muscle biopsy samples and still participate in the rest of the study. For these studies a muscle biopsy will be obtained as previously described⁷⁰ from the vastus lateralis muscle prior to the first EMS

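### The Friedman test for an EMS effect is not limited to the EMS period, so a change during care optimization alone could give P<0.05 for the five-visit outcomes

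*Combined protocol and SAP*

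**What the plan says.** Section 8 states: "There will be 5 measurements of the primary and most of the secondary outcome variables in each patient". The times are enrollment, after four weeks of care optimization (pre-EMS, Visit 2), weeks 8 and 16 of EMS, and four weeks after EMS ends. Changes over time are then to be "analyzed using the Friedman analysis of variance by ranks to determine if there was a statistically significant effect of EMS", at P<0.05. Section 8 names no subset of visits, no reference visit and no follow-up contrast.

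Section 4.1 defines the primary outcome as "the change in insulin resistance as determined by either HOMA-IR or LAR after 8 and 16 weeks of EMS training". It does not say from which visit the change is counted.

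Between enrollment and Visit 2 the team reviews dialysis care and may "make adjustments (if necessary) to meet standard of care guidelines" (section C.1, Overview, and Table 1). "Outcome markers will be reassessed again after completion of the 4-week care optimization phase", so a measurement directly before EMS exists.

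Elsewhere the plan keeps the periods apart. Section 4.2.11 compares blood pressure in the care-optimization "phase to that obtained during the EMS treatment and the 4-week post-EMS treatment phases to determine if EMS was associated" with a change. Section 4.2.1 gives the post-EMS strength visit its own question: "It will also determine how rapidly the effect on muscle strength is lost after stopping EMS training". Section 9.8 compares gene expression with the pre-EMS sample. None of these sections limits the Friedman test.

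**The concern.** The Friedman test is an omnibus test. On five visits its null hypothesis is that no visit differs from any other, and it has no reference visit. Of the four intervals between visits, only two lie within EMS training. The interval from enrollment to Visit 2 contains deliberate changes in dialysis care and no EMS. A lasting shift there makes enrollment differ from every later visit, which is enough to reject the null. Section 8 would then report that result as an effect of EMS.

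The trial is meant to give preliminary efficacy data for planning a larger randomized study. A P value that came from care optimization could be carried forward as evidence for EMS, although the plan already collects the visit that would separate the two.

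The concern covers HOMA-IR, LAR and the other outcomes measured five times. It does not cover peak VO₂ or DXA (three visits, starting at pre-EMS), blood pressure (its own phase comparison) or gene expression (its own paired test).

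**Working it through.** **1. Inputs.** From Section 8: n = 15, HOMA-IR mean 4.8 and SD 1.7, target fall 28%, significance level 0.05. Assumed, because the documents do not give them: within-patient correlation ρ = 0.5 between any two visits, normal data, a two-sided test, and the size of every pre-EMS shift.

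**2. The plan's own power figure.** Target difference = 0.28 × 4.8 = 1.344. SD of change = 1.7 × √(2(1 − ρ)) = 1.7 at ρ = 0.5. Noncentrality = 1.344 / 1.7 × √15 = 3.06 on 14 degrees of freedom. Paired t-test power = 81.2%, in line with the stated 80%. At ρ = 0.3 it is 67.3% and at ρ = 0.7 it is 95.6%, so ρ = 0.5 is the value consistent with the plan.

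**3. How a pre-EMS step reaches the five-visit test.** Q = 12 / (n k (k + 1)) × ΣR² − 3n(k + 1), where R is the rank sum of a visit, referred to chi-square with k − 1 degrees of freedom. Take the extreme case in which enrollment is the highest value in every patient and the other visits do not differ.
- Five visits: rank sums are 15 × 5 = 75 once and 15 × 2.5 = 37.5 four times. ΣR² = 5,625 + 4 × 1,406.25 = 11,250. Q = 12/450 × 11,250 − 270 = 30, against a critical value of 9.49.
- Visit 2, week 8 and week 16 only: rank sums are 30 each. ΣR² = 2,700. Q = 12/180 × 2,700 − 180 = 0, against 5.99.

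The five-visit test rejects strongly with nothing happening under EMS.

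**4. Realistic noise (simulation, at least 20,000 trials per case, no EMS effect, ρ = 0.5).**

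| Lasting fall between enrollment and Visit 2 | Five-visit Friedman | Visit 2, week 8, week 16 only |
|---|---|---|
| none | 4-5% | about 5% |
| 5% in every patient | 6% | about 5% |
| 10% in every patient | 12% | about 5% |
| 20% in every patient | 43% | about 5% |
| 10%, each patient with a 50% chance | 6% | about 5% |
| 20%, each patient with a 50% chance | 12% | about 5% |

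The last column holds for the three-visit Friedman test and for Holm-adjusted paired t-tests of weeks 8 and 16 against Visit 2. With other correlations, a 10% fall in every patient gives 10% (ρ = 0.3) or 19% (ρ = 0.7) on five visits.

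**5. Power for a true 28% fall at weeks 8 and 16, ρ = 0.5.** Five-visit Friedman 85-92%, depending on how much of the effect remains after EMS stops. Holm-adjusted pair 85-86% for at least one week (83% with Wilcoxon signed-rank tests). Single week-16 paired t-test 81%. Three-visit Friedman 72%.

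**The case against.** Section 8 never says that all five visits enter the test, and several sections lean toward a pre-EMS reference. That is true, so this is a gap in specification and not a demonstrated error. The five-visit reading is nevertheless the natural one. Section 8 lists the five times just before the test, and Sections 9.3, 9.5 and 9.6 tie all five measurements to the effect of EMS training. The word baseline does not settle it: it means enrollment in Section 5.1 and the pre-EMS measurement in Sections 9.2 and 9.8.

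The larger rejection rates need a sizeable shift in HOMA-IR in every patient. Table 1 has no glucose or insulin goal, and adjustments are made only where needed. This stands: no shift size is supported, and small or partial shifts leave the error near 5-6%.

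A reader might infer that a change after EMS stops is an equal source of false claims. The five-visit test would indeed respond to it. But if EMS does nothing, the documents give no reason for a change on stopping, and if EMS works, the loss is a consequence of EMS. The point does not rest on that interval.

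This is also a pilot: "Summary statistics will be used to describe and analyze the data", and values by visit would show a shift from enrollment to Visit 2. That limits the harm to the P value and its label. Section 8 still sets a significance threshold for an EMS effect, so the label matters.

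**Conclusion.** The point holds as a gap that should be fixed, with moderate weight. For the five-visit outcomes, the stated test as naturally read can be significant because of a change before any EMS, and it does not match the Section 4.1 endpoint. With an assumed correlation of 0.5 and normal data, the false-positive rate is about 6, 12 or 43% for an assumed lasting fall of 5, 10 or 20% in every patient, and about 6% for a 10% fall in about half of them. It is about 5% when the test is confined to Visit 2, week 8 and week 16. These figures show the mechanism and do not predict the result.

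A reader might go further and conclude that the trial will attribute care-optimization effects to EMS. The documents do not support that: they neither state that all five visits enter the test nor give any pre-EMS change in HOMA-IR or LAR.

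**What to change.** In Section 8, name Visit 2 as the reference and base the test of EMS only on Visit 2, week 8 and week 16, by one method fixed before the data are seen. The smallest change is the planned Friedman test on these three visits. An option is paired comparisons of week 8 and week 16 with Visit 2 (t or Wilcoxon signed-rank), Holm-adjusted. Report the change from Visit 2 with SD and 95% CI. Report enrollment to Visit 2, and week 16 to post-EMS, separately.

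This needs wording only, with no new visits or data. The cost is power. For a true 28% fall (normal data, correlation 0.5) it is about 72% with the three-visit Friedman or 85-86% with the Holm pair, against 85-92% for a five-visit test that does not isolate EMS. The advantage of the paired t-tests depends on normality: with skewed data (lognormal, assumed coefficient of variation 0.8) the Holm t-tests and the three-visit Friedman have 29% and 30% power. Holm covers the two weeks but not the two markers. Applied separately to HOMA-IR and LAR, it gives a family-wise error of about 7-9%, for assumed between-marker correlations from 0.8 down to 0.

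The plan should also state what the fix cannot do. Without a control arm it does not remove drift, regression to the mean, or care-optimization effects that continue after Visit 2. If half of a 10, 20 or 28% fall occurs by Visit 2 and the rest by week 8, the Holm pair rejects in about 8, 18 or 32% of trials with no EMS effect.

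A separate minor correction: Section 4.1 refers to randomization, which this single-arm plan does not have.

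### In this single-arm study a significant Friedman test shows change over time, and Section 8 should not read it as an effect of EMS

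*Combined protocol and SAP*

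**What the plan says.** Section C.1 describes one group. All patients go through four weeks of care optimization, in which the team may "make adjustments (if necessary) to meet standard of care guidelines as defined by CMS, KDOQI and KDIGO", and all then receive 16 weeks of EMS. Section 8 states "There will be 5 measurements of the primary and most of the secondary outcome variables in each patient": at enrollment, pre-EMS, weeks 8 and 16 of EMS, and 4 weeks after stopping. Changes over time are to be "analyzed using the Friedman analysis of variance by ranks to determine if there was a statistically significant effect of EMS", and "A P<0.05 will be considered statistically significant". Section 8 does not say which visits enter the test, and it gives the post-EMS visit no separate role.

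Off-treatment data have a stated use in two places. Section 4.2.11 compares blood pressure, pulse and hypotensive sessions across the pre-EMS, EMS and post-EMS phases. Section 4.2.1 says of the repeated strength measurements: "It will also determine how rapidly the effect on muscle strength is lost after stopping EMS training". DXA and peak VO2 are measured three times only, with no post-EMS value.

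**The concern.** The Friedman reference distribution treats each patient's visits as exchangeable. It contains no term for EMS. With one arm, rejection says that the visits differ and does not say why.

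The protocol itself contains other possible causes:

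- Dialysis care is adjusted just before EMS starts, and the consequences may still be developing during the EMS weeks.
- Patients are encouraged to exercise outside the dialysis unit (Section 2).
- Walk, strength and treadmill tests are repeated, so practice may improve them.

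If all five visits enter the test, a change completed during care optimization, before any EMS, also counts towards an EMS effect.

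At stake is the efficacy conclusion, and the effect size carried into the larger randomized trial that Section 8 says these data will help to plan.

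**Working it through.** **Inputs.** From Section 8: 15 patients, baseline HOMA-IR 4.8 (SD 1.7), a 28% decrease, P<0.05 (taken as two-sided). From Section 5, with window mid-points rounded: visits near Days -31, -3, 56, 112 and 145. Assumed: normal visit errors, independent within patient. The drift sizes are also assumed, because the protocol gives none.

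**1. The plan's own figure.** Section 8 claims "a sample size of 15 patients will provide 80% power to detect a 28% decrease in the HOMA-IR score". The calculation named there is a paired t-test.

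- Difference: 0.28 × 4.8 = 1.344.
- Taking 1.7 as the SD of the paired change, noncentrality = 1.344/1.7 × √15 = 3.06 on 14 df, critical t 2.145.
- Power 81%, so the claim reproduces.

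This uses a baseline SD as the SD of change, which amounts to a within-patient correlation of 0.5. The figure is for a paired t-test and not for the Friedman test. The matching SD for one visit is 1.7/√2 = 1.20.

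**2. Friedman rejection with no EMS effect.** Simulation, at least 20,000 trials per case, chi-square reference. Linear drift is the non-EMS fall from pre-EMS to week 16, continuing at the same rate over all visits used.

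| Drift as % of 1.344 | Pre, wk 8, wk 16 | Those plus post-EMS | All five |
|---|---|---|---|
| 0 | 5% | 5% | 5% |
| 25 | 8% | 10% | 13% |
| 50 | 18% | 28% | 45% |
| 75 | 36% | 58% | 83% |
| 100 | 58% | 85% | 98% |

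- A planned-size step that occurs wholly during care optimization is flagged in about 74% of trials with five visits, and in 5% once the enrollment visit is left out.
- The rates depend on the assumed correlation. At 0.8 instead of 0.5, the five-visit test flags a 25% drift in 28% of trials and a 50% drift in 86%.

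**3. What the post-EMS visit can add.** Take the mean of weeks 8 and 16 minus a weighted mean of pre-EMS and post-EMS.

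- Mean day on EMS: (56 + 112)/2 = 84.
- Pre-EMS weight w solves -3w + 145(1 - w) = 84, so w = 61/148 = 0.41, and the post-EMS weight is 0.59. Any linear trend then cancels.
- SD of the contrast: 1.20 × √(0.41² + 0.5² + 0.5² + 0.59²) = 1.21. Standard error: 1.21/√15 = 0.313.

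Under linear drift it rejects in 5% of trials at every drift size above. If a fraction p of a full EMS effect persists at the post-EMS visit, the expected contrast is 1.344 × (1 - 0.588p):

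| Persistence | Expected contrast | Power (one-sample t) |
|---|---|---|
| 0% | 1.34 | 98% |
| 25% | 1.15 | about 92% |
| 50% | 0.95 | about 80% |
| 100% | 0.55 | 38% |

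If only half the effect is present at week 8 and all of it persists, the expected contrast is 1.344 × (0.75 - 0.588) = 0.22 and power is 10%.

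**4. Where the contrast fails.** All with no EMS effect and a non-EMS change of planned size.

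- A step after the pre-EMS visit that persists: contrast 38%, three-visit Friedman 72%.
- Drift that levels off (assumed half-life 14 to 42 days): contrast about 34% down to 13%, depending on half-life and scaling.
- An influence that starts and stops with EMS: contrast 98%, three-visit Friedman about 72%. These data are identical to a fully reversible EMS effect.

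**The case against.** The strongest reply is that this is the ordinary limit of any uncontrolled study. A paired t-test would share it, and the sponsor calls the study a pilot meant to lead to a randomized trial. The plan also has partial safeguards: stratification by whether care goals were met (Section 4.1), regression of the change in HOMA-IR or LAR on training effect and EMS intensity (Sections 4.1 and 8), and the phase comparison for blood pressure (Section 4.2.11). All of that is true and it softens the point. None of these analyses tests whether the average change in HOMA-IR or LAR is more than drift, and Section 8 still attaches an EMS conclusion to P<0.05.

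A reader might infer more than the documents support:

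- **That any steady drift would be declared an EMS effect.** It would not. With 15 patients small drifts are usually missed, and the three-visit test misses even a drift of the full planned size in about 42% of trials.
- **That the post-EMS visit settles attribution.** It does not. A persistent non-EMS step and a persistent EMS effect produce the same data, which is why the contrast rejects in 38% of trials for both.
- **That the protocol expects every effect to fade within 4 weeks.** Section 4.2.1 says this of muscle strength only.
- **That the Friedman test is miscalibrated.** It holds its 5% level for its own null. The fault lies in the conclusion attached to it.

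**Conclusion.** The point holds as one of attribution. Section 8 equates change between visits with an effect of EMS, and in a single-arm design the planned test cannot support that step. The exposure ranges from slight to severe with the size of the non-EMS change and the visits included. It is about 8% rejection for a drift of a quarter of the planned effect over three visits, and about 98% for a drift of the full planned size over five. These figures rest on an SD of change of 1.7, independent normal visit errors and drift sizes that are assumptions.

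The scheduled post-EMS visit allows a useful supportive analysis. It does not replace a control arm. The change is worth making because it alters what the trial may conclude, although the pilot purpose limits the harm if it is not made.

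**What to change.** In Section 8:

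1. Report the Friedman result as change over time and not as an effect of EMS. Name the visits that enter it, and start from the pre-EMS visit so that change during care optimization is not counted.
2. For outcomes measured at the post-EMS visit (HOMA-IR, strength, 6-minute walk, cytokines and the others), prespecify the within-patient contrast: mean of weeks 8 and 16 minus about 0.41 × pre-EMS plus 0.59 × post-EMS, the two weighted values being added before subtraction. Give the estimate, a 95% CI and a one-sample t or signed-rank test, labelled as supportive. For LAR, first confirm that leptin and adiponectin will be assayed at that visit, because the blood lists in Section 5 name insulin and glucose but not these two.
3. State the limits beside the result. The contrast removes only linear drift. It cannot separate a persistent non-EMS step, or an influence that starts and stops with EMS. It loses power if the EMS effect persists. It should not be a gate for interpretation, and a null contrast is not evidence of no effect.
4. For peak VO2 and DXA, report change over time only.

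The cost is revised wording and one extra contrast per outcome on visits already scheduled. The possible exception is the LAR assays, if they are not already planned at the post-EMS visit.
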